3.1 Study design

This is a randomized controlled, multicenter, 12 month study of Lucentis (ranibizumab) that the consenting patients will participate in a screening period and will be evaluated for their eligibility to enroll the study. After the screening period and the eligibility assessment of the patient, only one eye will be selected / treated as the study eye. After eligibility confirmation at baseline, patients will be randomized into one of the treatment arms as below:

- Arm 1 - Labeled regime arm: Treatment will be given monthly and will be continued until maximum visual acuity is achieved (the patient's visual acuity is stable for three consecutive monthly assessments performed while on ranibizumab treatment). Thereafter patients should be monitored monthly for visual acuity.
- Retreatment criteria:
 - According to this protocol VA stability means BCVA \geq 84 letters (approximate Snellen equivalent of 20/20) or OCT <300 microns in the last 2 consecutive visits or no improvement can be achieved according to the investigators evaluation regarding VA and OCT measures in the last 2 visits . Stable patients do not require reinjection and should be evaluated in the next visit for reinjection.
 - If VA decreases \geq 5 letters compared to previous visit and OCT is >300 microns, patients will be retreated.
 - If VA decreases \geq 5 letters compared to the previous visit or CRT increases >50 microns compared to the previous visit, patients will be retreated.
 - After 3 monthly injections of the investigational drug laser photocoagulation can be administered if VA worsens \geq 10 letters and/or CRT increases >100 microns.
- The interval between two doses should not be shorter than 1 month.
- Arm 2 - Wait and Extend regime arm: Lucentis (ranibizumab) 0.5 mg will be injected subsequently at baseline, month 1 and 2. After the three initial loading doses, patients will be called for the control visits 1 month later. If the visual acuity has reached a stable level and there is no sign of edema on OCT, patients will not receive intravitreal injection and will be called to come back 6 weeks later. The interval is increased by 2 weeks until a maximum of 8 weeks as long as the patient presents as stable regarding visual acuity, central retinal thickness and clinical findings. If there is a negative change, the interval is shortened back to 4 weeks.

Retreatment criteria:

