- According to this protocol VA stability means BCVA \geq 84 letters (approximate Snellen equivalent of 20/20) or OCT <300 microns in the last 2 consecutive visits or no improvement can be achieved according to the investigators evaluation regarding VA and OCT measures in the last 2 visits . Stable patients do not require reinjection and should be evaluated in the next visit for reinjection.
- If VA decreases \geq 5 letters compared to previous visit and OCT is >300 microns, patients will be retreated.
- If VA decreases \geq 5 letters compared to the previous visit or CRT increases >50 microns compared to the previous visit, patients will be retreated.
- After 3 monthly injections of the investigational drug laser photocoagulation can be administered if VA worsens \geq 10 letters and/or CRT increases >100 microns.

Figure 3-1 Study design

Study Design For Labelled Regime Arm

Phase	Screening		Main Treatment			
Visit	1	2	3	4	5	6 -14
Month	0		1	2	3	4 – 12
Day	-7 to -1	B	30	60	90	120 – 360

Study Design For Wait and Extend Arm

Phase	Screening		Main Treatment			
Visit	1	2	3	4	5	Visit number may vary according to the response of the patient
Month	0		1	2	3	4 – 12
Day	-7 to -1	B	30	60	90	120 – 360

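### In Arm 2, one rule ties withholding an injection to absence of edema on OCT while the same arm's stability definition does not, and nothing says which governs an eye with unchanged residual edema

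*Protocol*

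**What the plan says.** **The condition for withholding and extending.** In protocol 3.1, Arm 2 eyes receive ranibizumab that "will be injected subsequently at baseline, month 1 and 2" and are seen again one month later. At that point: "If the visual acuity has reached a stable level and there is no sign of edema on OCT, patients will not receive intravitreal injection"; the patient then returns after 6 weeks. The synopsis and protocol 5.2 carry the same condition. SAP section 4 carries it in similar words. None of these three gives a definition of stability.

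**Later extension.** Protocol 3.1 continues: "The interval is increased by 2 weeks until a maximum of 8 weeks as long as the patient presents as stable". Stability here covers acuity, retinal thickness and clinical findings. Absence of edema is not mentioned. The reverse step is: "If there is a negative change, the interval is shortened back to 4 weeks".

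**The stability definition.** Under the retreatment criteria for the same arm, 3.1 defines stable acuity as BCVA of at least 84 letters, "or OCT <300 microns in the last 2 consecutive visits or no improvement can be achieved according to the investigators evaluation". The consequence is: "Stable patients do not require reinjection and should be evaluated in the next visit for reinjection".

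**Retreatment triggers.** These compare with the previous visit: a loss of 5 or more letters, or "CRT increases >50 microns compared to the previous visit, patients will be retreated".

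**A third test.** Footnote d to the visit schedule in protocol section 6 makes the post-loading injections depend on whether the lesion is active. It points to an outside college's criterion that the protocol does not set out.

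**The concern.** The first rule has two conditions, stable acuity and no edema. The stability definition attaches the same consequence, no injection, to stability alone. The alternative of 84 letters or more and the alternative "no improvement can be achieved according to the investigators evaluation regarding VA and OCT measures in the last 2 visits" can both be met by an eye that still has edema. For those eyes the two rules point in different directions.

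The rule is part of what defines the experimental regimen. The numbers of injections and visits under wait and extend are two secondary objectives (protocol 2.2, SAP 6.14.3), and drug exposure lies behind the Month-12 BCVA and CRT. Protocol 6.3 counts a patient as fully compliant when injections are given as planned, and 9.3 reports that proportion. For the eyes in question the plan can be read two ways, so neither compliance nor a deviation can be classified.

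Little in the design would bring sites to one reading. The study is open-label (5.4), runs at about 12 centers (section 4), has OCT evaluated by each site's own staff (6.4), and has no adjudication committee (8.5).

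**Working it through.** The documents give no expected number of Arm 2 injections, so there is no plan figure to reproduce. The nearest is the visit schedule, which marks 10 conditional injection cells after Month 2 (Months 3 to 12).

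**Step 1. Apply each rule to one eye.** Take an eye after loading with residual edema on OCT, for example 400 microns, the same at each visit. Acuity is unchanged and the investigator judges that no further improvement can be had.

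- Withholding condition: acuity stable, yes; no edema, no. Condition not met.
- Stability definition: third alternative met. No reinjection required.
- Triggers: letters lost, 0 (5 needed); CRT rise, 0 microns (more than 50 needed). Neither fires.
- Later extension clause: retinal thickness is stable. Edema is not asked about.
- Footnote d: cannot be applied, because an active lesion is not defined.

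An eye with 84 letters or more and unchanged residual edema gives the same result through the first alternative. The alternative of OCT below 300 microns may largely coincide with no edema, so the conflict rests on the other two.

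**Step 2. Injections after the last loading dose (Day 60), up to Day 360.**

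- Edema condition read as a requirement, monthly visits at 30-day spacing: Days 90 to 360, (360 − 90)/30 + 1 = 10. At 28-day spacing: Days 88 to 340, (340 − 88)/28 + 1 = 10. If no injection is given at the Month-12 visit on 30-day spacing, 9.
- Injected at every visit, but the interval extended because the eye is stable: Days 90, 132, 188, 244, 300, 356 (steps of 42, then 56 days), so 6.
- Stability definition applied at every visit, no trigger ever firing: 0.

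With the three loading doses the totals are 13, 9 and 3 respectively (taking 10, 6 and 0).

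**Step 3. Visits after Day 60.**

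- Monthly throughout: 10 at 30-day spacing, Month 12 included; 11 at 28-day spacing with a separate Month-12 visit.
- Extended: 6 (the dates above; Day 356 is within 7 days of Day 360).
- Difference: 10 − 6 = 4 or 11 − 6 = 5 if the uninjected eye is extended, and 0 if it stays on monthly visits.

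**Step 4. Effect on the arm mean.** Shift = share of such patients × difference per patient. For a share of 10%:

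- injections: 0.10 × 10 = 1.0 at most; 0.10 × 6 = 0.6 on the extended schedule;
- visits: from 0.10 × 0 = 0 to 0.10 × 5 = 0.5.

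The share is not in the documents; 10% is a unit for scaling, not an estimate.

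**The case against.** **The condition says if, not only if.** It states when an injection is withheld. It does not say that an eye with stable acuity and residual edema must be injected, and no text gives an explicit instruction for that eye. SAP section 4 comes closest to implying continued injection, but sets no schedule. This stands, and it makes the upper count an inference. It does not remove the problem: if the edema clause does not restrict withholding, it has no function.

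**The condition may govern only the first control visit, with the retreatment criteria taking over later.** This is possible, but the stability definition is worded for the protocol as a whole and carries no such limit. On this reading there is still no statement of what happens at the first control visit to an eye that fails the condition, or when it returns.

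**The extended visit schedule is not set by the stability definition.** This is correct. That definition refers only to the next visit. The first step to 6 weeks appears only in the sentence that also requires no edema. The visit effect is therefore a range that starts at zero.

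**The extremes are unlikely to persist.** Zero injections needs an edematous eye, off drug for about nine months, never to lose 5 letters or thicken by more than 50 microns between visits. Ten needs an unbroken plateau with an injection at every monthly visit. This also stands.

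**Much can be reconstructed.** Doses are tracked on the CRF at each visit (5.5.4), BCVA and OCT are scheduled at every post-baseline visit, and SAP 6.11 tabulates macular edema on OCT. Only the investigator's no-improvement judgement would be new. This limits the harm to interpretation, but it shows afterwards what sites did, not what the plan asked for.

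**Conclusion.** The point holds as an unresolved conflict about one type of Arm 2 eye: 84 letters or more, or a plateau, with unchanged residual edema. The withholding condition, the stability definition, the later extension clause and footnote d do not agree for that eye, and nothing ranks them. It blurs the definition of the tested regimen and the interpretation of the injection and visit counts for such eyes.

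The size is illustrative: about 6 to 10 post-loading injections against 0. This rests on reading the edema condition as a requirement on one side, and on no trigger ever firing on the other. Per 10% of Arm 2 patients in this state, the arm's mean could move by up to about 1.0 injection and by 0 to 0.5 visit. The effect on the trial cannot be put at a figure, because the share is unknown.

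Two stronger readings are not supported. A reader might infer that the protocol orders 10 injections in one place and none in another; it does not, since the first figure is implied and both are extremes. A reader might also infer that neither the non-inferiority result nor the counts could be attributed to any defined regimen. That goes too far: the ambiguity lies at one decision point, some investigator discretion is expressly part of the regimen, and most of the relevant data are collected.

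**What to change.** Reconcile the protocol synopsis, 3.1 (the Arm 2 description and its retreatment criteria), 5.2, footnote d of the visit schedule and SAP section 4 into a single statement for Arm 2. It should say when an injection is withheld, when the interval is extended, and whether residual edema prevents either. Use it in the same words in each place, and either define the active-lesion test or remove it. Which clinical rule to adopt is the sponsor's decision.

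Add one CRF item recording, at each Arm 2 visit, which criterion led to injection, withholding or extension. The injection and visit counts can then be interpreted, and the share of eyes in this state reported.

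The cost is a wording amendment and one CRF field, with no extra patients or procedures.

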3.2 Rationale of study design

A “wait and extend” regimen has been demonstrated efficient for treatment of wAMD in SALUTE study as mentioned above and found to be safe and tolerable. The rationale of this pilot study is to show that similar approach is applicable in treatment of DME.

3.3 Rationale of dose/regimen, route of administration and duration of treatment

The dose, dose regimen, titration scheme and tapering-off scheme, etc. are in accordance with product labeling in Arm 1. Since a “wait and extend” regimen has been demonstrated efficient for treatment of wAMD in SALUTE study and found to be safe and tolerable, it was decided to show the similar approach for the treatment of DME.

3.4 Purpose and timing of interim analyses/design adaptations

There will be no interim analysis.

3.5 Risks and benefits

The risk to subjects in this trial will be minimized by compliance with the inclusion/exclusion criteria, close clinical monitoring, since the study has been designed in a similar approach to a newly completed study which was completed with no major safety and tolerability concerns there are no unknown risks to *Ranibizumab* which may be serious and unforeseen.

4 Population

The study population will consist of male and female patients (over 18 years old) admitted to hospital with Type 1 or Type 2 diabetes mellitus (according to ADA or WHO guidelines) with HbA1c not more than 12.0% at screening (Visit 1). Patients should be on diet, exercise, and/or pharmacological treatment for diabetes and should have a visual impairment due to focal or diffuse macular edema with center involvement in at least one eye, as demonstrated with color fundus photography, fluorescein angiography and OCT within 28 days of the baseline treatment. It is aimed to randomize a total of 86 patients in approximately 12 centers in Turkey. Since a 20% screening failure rate is expected, 104 patients have to be screened.

4.1 Inclusion criteria

Patients eligible for inclusion in this study have to fulfill **all** of the following criteria:

1. Written informed consent must be obtained before any assessment is performed.
2. Male or female patients >18 years of age who have signed an informed consent
3. Patients with Type 1 or Type 2 diabetes mellitus (according to ADA or WHO guidelines) with HbA1c not more than 12.0% at screening (Visit 1). Patients should be on diet, exercise, and/or pharmacological treatment for diabetes.
4. Patients with visual impairment due to focal or diffuse macular edema with center involvement in at least one eye, as demonstrated with color fundus photography, fluorescein angiography and OCT within 28 days of the baseline treatment. If both eyes are eligible, the one with the worse visual acuity, as assessed at Visit 1, will be selected for study treatment unless, based on medical reasons, the investigator deems the other eye the more appropriate candidate for study treatment. The study eye must fulfill the following criteria at Visit 1:
 - BCVA score between 78 and 39 letters, inclusively, using ETDRS-like visual acuity testing charts at a testing distance of 4 meters (approximate Snellen equivalent of 20/32 to 20/160)
 - Decrease in vision is due to DME and not due to other causes, in the opinion of the investigator

4.2 Exclusion criteria

Patients fulfilling **any** of the following criteria are not eligible for inclusion in this study. No additional exclusions may be applied by the investigator, in order to ensure that the study population will be representative of all eligible patients.

1. Concomitant conditions in the study eye according to defined criteria such as infection, inflammation, uncontrolled glaucoma
2. Active proliferative diabetic retinopathy or evidence of vitreomacular traction. in the study eye
3. Patients who are monocular or have a BCVA score in the non-study eye (fellow eye) \leq 24 letters (approximate Snellen equivalent of 20/320) at Visit 1
4. The history of vitrectomy in the study eye.
5. Concomitant systemic condition according to defined criteria, eg. history of stroke, uncontrolled diabetes, renal failure, unsatisfactory controlled hypertension
6. Use of other investigational drugs within 5 half-lives of enrollment, or within 30 days until the expected PD effect has returned to baseline, whichever is longer.
7. History of hypersensitivity to any of the study drugs or to drugs of similar chemical classes.
8. History of malignancy of any organ system (other than localized basal cell carcinoma of the skin), treated or untreated, within the past 5 years, regardless of whether there is evidence of local recurrence or metastases.
9. Pregnant or nursing (lactating) women, where pregnancy is defined as the state of a female after conception and until the termination of gestation, confirmed by a positive hCG laboratory test.

Women of child-bearing potential, defined as all women physiologically capable of becoming pregnant, unless they are using effective methods of contraception during dosing of study treatment. Women are considered post-menopausal and not of child bearing potential if they have had 12 months of natural (spontaneous) amenorrhea with an appropriate clinical profile (e.g. age appropriate, history of vasomotor symptoms) or have had surgical bilateral oophorectomy (with or without hysterectomy) or tubal ligation at least six weeks ago. In the case of oophorectomy alone, only when the reproductive status of the woman has been confirmed by follow up hormone level assessment is she considered not of child bearing potential.

5 Treatment

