5.5.8 Prohibited Treatment

Any concomitant medications including prescription drugs or over-the-counter preparations used by a patient during the study and until the conclusion of the study participation (except for routine medications given for ocular procedures required by the protocol, i.e. fluorescein, dilating drops, topical antibiotic, topical anesthetic) must be recorded on the Concomitant medications/Significant non-drug therapies CRF including start and stop dates and reason for use.

Laser photocoagulation for DME is permitted only as rescue treatment according to predefined criteria and needs to be

recorded on the Concomitant medications/Significant non-drug therapies CRF

Use of the following treatments is NOT allowed after the start of the study:

- Chronic concomitant therapy with topical ocular corticosteroids
- Other intravitreal medication in the study eye
- Systemic medications known to be toxic to the lens, retina or optic nerve, including Deferoxamine, Chloroquine/ hydroxychloroquine (Plaquenil), Tamoxifen, Phenothiazines and Ethambutol
- Treatment with glitazones during the study.
- Any other investigational drug

The below treatments will be prohibited 30 days before randomisation: verteporfin (Visudyne®), external beam radiation treatment, , submacular surgery or other surgical interventions for DME.

The below treatments will be prohibited 90 days before randomisation: focal laser photocoagulation treatment.

The below treatments will be prohibited 120 days before randomisation: macular laser photocoagulation treatment.

During the study, below treatment will be permitted: Retrobulber anesthesia to prevent eye movements, metochloropamide or other treatments for preventing the nausea due to fluorescein injection and other routine treatments for glaucoma. The patient will also be provided an additional topical antimicrobial medication to use 3 days after the injection which will be used 4 times a day.

If the investigator decided that the other eye (other than the study eye) has a DME lesion or has a new DME lesion occurred during the study which needs treatment, appropriate routine ranibizumab treatment will be applied by the investigator; however any data will not be collected for the other eye. The ranibizumab treatment applied to the other eye will be given by NOVARTIS.

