9.7 Sample size calculation

A sample size of 86 (43 for each treatment arm) can achieve 90% power to detect non-inferiority limit of 5 letter between treatment arm when significance level of the test is 0.025 and the mean (standard deviation) letter change of labeled regime arm will be around 7 (7). To eliminate the effects of incomplete data which are expected in 1 year follow-up period, a priori 20% of drop-out rate is accepted; therefore at least 104 patients (52 for each treatment arm) will be included to the study.

10 Ethical considerations**10.1 Regulatory and ethical compliance**

This clinical study was designed and shall be implemented and reported in accordance with the ICH Harmonized Tripartite Guidelines for Good Clinical Practice, with applicable local regulations (including European Directive 2001/20/EC, US Code of Federal Regulations Title 21, and Japanese Ministry of Health, Labor, and Welfare), and with the ethical principles laid down in the Declaration of Helsinki.

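### Earlier intravitreal anti-VEGF or steroid in the study eye is neither excluded, given a look-back, stratified for nor adjusted for, so change from baseline is harder to interpret

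*Protocol*

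**What the plan says.** Protocol 4.2 gives nine exclusions. The only drug washout among them, no. 6, covers other investigational drugs. The list is closed to sites: "No additional exclusions may be applied by the investigator".

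Protocol 5.5.8 handles other treatments in two ways. One list opens with "Use of the following treatments is NOT allowed after the start of the study" and includes other intravitreal medication in the study eye. It has no look-back. Separate sentences set periods before randomisation: 30 days for verteporfin, external beam radiation and surgery for DME, 90 days for focal laser, and finally "The below treatments will be prohibited 120 days before randomisation: macular laser photocoagulation treatment". The terms focal and macular laser are not defined or distinguished.

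Protocol 4.1 requires a study-eye BCVA of 39 to 78 letters at Visit 1, vision loss due to DME, and centre-involving oedema on imaging within 28 days of the baseline treatment. The schedule in section 6 places OCT, angiography and fundus photography at Visit 1 (day -7 to -1).

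Randomisation is 1:1 with no stratification factor named (5.3). SAP 6.14.1 compares the change in BCVA between arms with an unadjusted Mann-Whitney test. Neither document defines a covariate or subgroup for earlier treatment.

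**The concern.** The protocol controls earlier laser, surgery, radiation and verteporfin, but not earlier use of the drug class under test. Section 1.1 describes ranibizumab as approved for DME in a number of countries, and 5.5.8 provides for routine ranibizumab in the fellow eye. Previously injected eyes are therefore a realistic part of the recruitment pool.

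The primary variable is change from baseline. If part of an eye's response came before baseline, its measured gain no longer reflects the full effect of the regimen. The mean gain could fall below the 7 letters assumed in 9.7 and the SD could rise. If such eyes also respond more alike under the two regimens, the trial is less able to detect a real deficit, which matters most in a non-inferiority comparison. The planned analysis has no means of showing whether this happened.

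**Working it through.** **1. The plan's own figure.** Protocol 9.7 states: "A sample size of 86 (43 for each treatment arm) can achieve 90% power to detect non-inferiority limit of 5 letter", with SD 7, and "significance level of the test is 0.025". Taking alpha as one-sided and the true difference as 0:

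n per arm = 2 × 7² × (1.960 + 1.282)² / 5² = 98 × 10.51 / 25 = 41.2, so 42 per arm by the normal approximation. The noncentral t gives 43 per arm with 90.6% power. The stated 86 is reproduced. The standard error of the difference is 7 × √(2/43) = 1.51 letters.

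The documents give neither the share of pre-treated eyes, f, nor the size of any carry-over. Everything below is an assumption range. It also assumes a t-test against the 5-letter margin, which the SAP's Mann-Whitney comparison is not.

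**2. Carry-over as a pure baseline shift.** Suppose earlier treatment raises the baseline by c letters in a fraction f of eyes in both arms. The shift cancels, in expectation, in the difference of mean changes. What moves is:

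- mean gain = 7 − f × c
- SD = √(49 + f(1 − f)c²)

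| f | c | mean gain | SD | power at 43 per arm |
|---|---|---|---|---|
| 0 | – | 7.0 | 7.00 | 90.6% |
| 10% | 3 | 6.7 | 7.06 | 90.1% |
| 20% | 5 | 6.0 | 7.28 | 88.3% |
| 30% | 7 | 4.9 | 7.70 | 84.5% |
| 50% | 7 | 3.5 | 7.83 | 83.4% |

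Under this mechanism non-inferiority becomes slightly harder to show. The larger SD already contains the chance imbalance between arms. At f = 20% and c = 5 that component has SD 5 × √(2 × 0.2 × 0.8/43) = 0.43 letters.

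**3. Carry-over that also changes the regimen difference.** Suppose the true deficit is 5 letters in untreated eyes and 5(1 − k) in pre-treated eyes, where k is the fraction of the deficit lost. The overall deficit is d = 5(1 − f × k). The chance of declaring non-inferiority at 43 per arm and SD 7 (noncentral t) is:

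| f | d, k = 1 | chance | d, k = 0.5 | chance |
|---|---|---|---|---|
| 0 | 5.0 | 2.5% | 5.0 | 2.5% |
| 10% | 4.5 | 5.1% | 4.75 | 3.6% |
| 20% | 4.0 | 9.6% | 4.5 | 5.1% |
| 30% | 3.5 | 16.4% | 4.25 | 7.1% |
| 50% | 2.5 | 37.3% | 3.75 | 12.7% |

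The normal approximation, Φ((5 − d)/1.51 − 1.96), gives 5.2%, 9.7% and 16.7% for k = 1 at 10%, 20% and 30%. These are chances of a favourable conclusion when the deficit in *untreated* eyes lies at the margin. They are not type I error rates for the mixed population, whose true deficit (3.5 letters at f = 30%, for example) is inside the margin.

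**4. The laser terms.** An eye that had focal laser to the macula 100 days before randomisation satisfies the 90-day rule and fails the 120-day rule. The text does not say which applies.

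**The case against.** The strongest objection concerns bias. A reader might infer that carry-over is built into the baseline and pulls the comparison toward no difference. The documents do not support that. Carry-over is permitted, not planned. The entry criteria limit it, because an eye that responded well to recent injections may no longer show impaired vision and oedema. Randomisation balances prior treatment in expectation, and a common shift cancels. A pull toward similarity needs a smaller regimen difference in pre-treated eyes, which no section states. The reverse is also possible, since an eye with a raised baseline has more to lose if later under-treated. This objection stands, and the point therefore asserts no direction of bias.

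Three other inferences also go too far:

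- **That a site following 4.2 must enrol an eye that 5.5.8 prohibits.** Section 4.2 bars exclusions added by the investigator, and the 5.5.8 look-backs are the protocol's own rules. The missing cross-reference is a drafting weakness.
- **That a recent pre-study ranibizumab dose breaches the rule "The interval between two doses should not be shorter than 1 month".** In 3.1 that sentence closes the Arm 1 description, and nothing extends it to doses before the study.
- **That injection counts are understated.** The objective counts injections over the 12-month treatment period, so earlier doses fall outside it by definition.

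It can also be said that 6.2 already collects ocular history and applied treatments. That is partly true, but it does not explicitly ask for the type and date of the last study-eye treatment, and no analysis uses it.

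None of this closes the gap itself. 5.5.8 has no look-back for intravitreal drugs that a site could apply. The freedom in 4.1 to choose the other eye for medical reasons helps only when both eyes qualify.

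**Conclusion.** The gap is certain from the text. A recently injected eye that meets the other entry criteria is eligible, cannot be refused on that ground, and is not distinguished in the analysis. Change from baseline is harder to interpret as a result, and assay sensitivity may be reduced.

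The consequence is not determinable. With 10% to 30% pre-treated eyes, the chance of declaring non-inferiority despite a 5-letter deficit in untreated eyes ranges from 2.5% (no change in the regimen difference), through about 4% to 7% (half the deficit lost), to about 5% to 17% (deficit wholly absent, the extreme case). If only the baseline moves, by 3 to 7 letters, the cost is a fall in power from 90.6% to no lower than 84.5%. All of this rests on assumed shares and effects, 43 evaluable eyes per arm, SD 7 and a margin-based test.

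This is a moderate weakness that is worth correcting. It does not invalidate the design, and the stated sample size does not change.

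**What to change.** - **Protocol 4.2:** state a criterion for earlier intravitreal anti-VEGF or corticosteroid in the study eye, with a look-back that the sponsor sets and justifies. Cross-reference the 5.5.8 look-backs so that all eligibility rules can be found in one place.
- **Protocol 5.5.8:** define focal and macular laser and reconcile the 90-day and 120-day rules.
- **Protocol 6.2 and CRF:** record explicitly the type and date of the last treatment to the study eye.
- **SAP 6.14.1:** prespecify a BCVA analysis adjusted for prior treatment, for example a linear model with arm, baseline BCVA and prior treatment, giving a confidence interval to set against the 5-letter margin. Report the arm difference separately for pre-treated and untreated eyes. Adjustment alone does not reveal a regimen effect that differs between the two groups; the separate results address that. They will be imprecise: at a 20% share there are 0.2 × 43 = 8.6 eyes per arm, with a standard error of 7 × √(2/8.6) = 3.4 letters, so they should be labelled descriptive.

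The cost is one protocol amendment, one CRF field, a short SAP addition, and slightly slower recruitment if recently treated eyes must wait or be refused.
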